This is a Phase 1b/Phase 2a, open-label, multicenter study to determine the safety, tolerability, RP2D, efficacy, pharmacokinetics (PK) and pharmacodynamic (PD) properties of idronoxil when rectally administered as a suppository (NOX66) to patients with any solid tumor (Part 1) and patients with mCRPC, BC and non-small-cell lung cancer (NSCLC) (Part 2) who are eligible for low-dose EBRT for at least one symptomatic or minimally symptomatic lesion (for the prevention of symptoms). The study is divided into 2 parts: Part 1 (dose escalation) and Part 2 (dose expansion). The study design allows an exploration of different doses of NOX66 (800 mg, 1200 mg, 1600 mg and 2400 mg) with safety monitoring to ensure the safety of the patients. A Safety Steering Committee (SSC) will review available safety data after the first cycle (21 days) of each dose cohort of NOX66 in Part 1 to determine the maximum tolerated dose (MTD)/RP2D.

In Cycle 1, NOX66 will be administered for 14 days followed by a 7-day rest period on a 21-day cycle. From Cycle 2 onwards, NOX66 will be administered for 7 days followed by a 7-day rest period on a 14-day cycle. Patients will continue to receive NOX66 on a cyclical basis until disease progression, unacceptable toxicity, withdrawal of consent, start of a new anticancer therapy, withdrawal of the patient by the Investigator or termination of the study by the Sponsor.

The study population consist of patients with mCRPC, BC, NSCLC or other solid tumors who have failed at least one line of prior treatment and for whom, according to the Investigator, are eligible for low-dose EBRT for at least one symptomatic or minimally symptomatic lesion (for the prevention of symptoms).

The dose levels of EBRT will be either:

- 8 Gray (Gy) as a single fraction, or
- 20/25 Gy as 5 fractions given over 5 to 10 days.

The first EBRT dose fraction must be administered on Day 2 of Cycle 1 and the remaining dose fractions will be given between Day 3 and Day 11. The choice of one of the EBRT dose/fractions stated above will be at the discretion of the Investigator and will be determined by the clinical requirements of the patient. EBRT will be administered according to the institutional protocol.

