Pharmacokinetic Measurem	ent												
Blood sample for PK ^z	Х		Х	Х		Х							
Pharmacodynamic Biomark	ker As	sessment							-				
Blood sample for biomarkers ^{aa}			Х								Х		
Archived tissue collection if available (Optional) ^{bb}													
Fresh tissue biopsy after Cycle 3 treatment (Optional) ^{bb}						х							
Treatment Administration													
NOX66 ^{cc}	Х	Х		Х	Х		Х	Х		Х			
EBRT (1-10 days) dd													

AE = adverse event; BPI-SF = Brief Pain Inventory – Short Form; C1D1 = Cycle 1, Day 1; COVID-19 – coronavirus disease 2019; CT = computerized tomography; d = day(s); EBRT = external beam radiotherapy; ECG = electrocardiogram; ECOG = Eastern Cooperative Oncology Group; ED = Early Discontinuation; EORTC-QLQ-C30 = Quality of life Questionnaire for Cancer Patients; EOT = End of Treatment; FACT-P: Functional Assessment of Cancer Therapy – Prostate; FSH = follicle-stimulating hormone; Gy = Gray; mCRPC = metastatic castration-resistant prostate cancer; MRI = magnetic resonance imaging; PCWG-3 = Prostate Cancer Working Group 3; PEQ = Patient Experience Questionnaire; PK = pharmacokinetics; PRO = Patient Reported Outcome; PSA = prostate-specific antigen; RECIST = Response Evaluation Criteria in Solid Tumors; SAE = serious adverse event; SARS-CoV-2 = severe acute respiratory syndrome coronavirus 2; SRE = skeletal-related events; SSE = symptomatic skeletal events; WBC = white blood cell; WOCBP = women of childbearing potential

- † Patients will receive the study drug from Cycle 1 Day 1 and may continue to receive the study drug until disease progression, unacceptable toxicity, withdrawal of consent, start of new anticancer therapy, withdrawal of the patient by the Investigator or termination of the study by the Sponsor.
- ‡ From Cycle 3 onwards, study drug for 2 cycles will be dispensed every second cycle (i.e., Cycles 5, 7, 9, 11 etc.). From Cycle 5 onwards, on-site visits will occur on a 28-day (4 weekly) basis, i.e., patients will visit the clinical unit every second cycle. After Cycle 5, the next on-site visit will therefore be Cycle 7, followed by Cycle 9, etc. until the patient completes the study treatment period or discontinues from the study, whichever comes first.
- § The procedures listed and schedule followed for Cycle 4 will be assessed at all cycles without an on-site visit (unless otherwise specified).

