- * The procedures detailed at Cycle 5 Day 1 will be performed for all subsequent on-site visits (unless otherwise specified). Patients will continue NOX66 administration in each cycle from Day 1 until Day 7 followed by a 7-day rest period (Days 8 to 14).

It is important that PK sampling occurs as close as possible to the scheduled time. In order to achieve this, other assessments scheduled at the same time may be initiated prior to the timepoint. The order of assessments (as applicable to study visit) that should occur before dosing is: 1) PRO questionnaires, 2) vital signs, 3) ECG, 4) PK sampling, 5) dose administration. Blood sampling for safety laboratory assessments will be done prior to dosing. The order of assessments (as applicable to the study visit) that should occur after dosing is: 1) vital signs, 2) ECG, 3) PK sampling. All other procedures can be completed (as applicable to study visit) after the PK sample has been collected. It is critical that the patients record the time of dose in their Patient Study Drug Administration Diary for the PK assessment and the site record the time of blood sampling.

- ^{a.} End of Treatment Visit (EOT) occurs 7 to 10 days after the last dose of study drug. Assessments completed within 7 days prior to the last dose of study drug do not need to be repeated. If a patient discontinues from the study early (Early Discontinuation [ED]), they will have an ED Visit within 7 to 10 days after the last dose of study drug.
- ^{b.} For patients who permanently discontinue study drug for any reason other than confirmed disease progression, tumor imaging and disease response assessments will continue to be performed every 12 weeks (± 7 days) for up to 12 months after the last dose of the study drug until disease progression, withdrawal of consent, initiation of new anticancer therapy, the patient is lost to follow-up or death, whichever comes first.
 - If a patient meets disease progression during the follow-up period according to RECIST v1.1 criteria, a tumor imaging and disease response assessment is not required.
 - If a patient permanently meets clinical disease progression during the follow-up period, a tumor imaging and disease response assessment does not need to be repeated if completed ≤ 28 days after the date of clinical disease progression.
 - Patients who have met disease progression will be contacted every 3 months for survival follow-up.

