- ^{o.} Testosterone levels of ≤ 14.4 ng/dL must be maintained from baseline and throughout the study. Testosterone levels will be measured at Screening, on Day 1 of Cycles 1, 2 and 3, every second cycle thereafter (i.e., Cycles 5, 7, 9, 11 etc.) and at the EOT/ED Visit.
- P. Serology: hepatitis B surface antigen, hepatitis B core antibody, hepatitis C antibody and human immunodeficiency virus. Testing only applicable to patients who have a past history of viral hepatitis or in whom there is a current suspicion of viral hepatitis, or who are considered to be at risk for human immunodeficiency virus infection.
- ^q Optional: SARS-CoV-2 testing to be done at Screening and additional time points. Testing to be done if medically indicated and at the discretion of the Investigator. SARS-CoV-2 testing is not required during the follow-up period. Patients will be advised about the risks of COVID-19 infection and will be questioned by phone call prior to each on-site visit to assess their health and/or contact with persons who tested positive for COVID-19 infection.
- ^{r.} Postmenopausal women only.
- ^{s.} Only applicable to women of childbearing potential (WOCBP). Serum pregnancy test to be performed at Screening and urine pregnancy test to be performed prior to Day 1 of Cycles 1 to 3, at every second cycle thereafter (i.e., Cycles 5, 7, 9 11 etc.) and at the EOT/ED Visit. No pregnancy testing will be performed after this period. WOCBP must continue using approved contraception methods for at least 3 months after discontinuation of the study drug. During the follow-up period, WOCBP will be questioned about their pregnancy status and use of contraception up to 3 months after last dose of study drug.
- t At each on-site visit the study staff will question the patient about all adverse events (AEs) experienced since their last on-site visit. Information on AEs and serious adverse events (SAEs) will be collected from signing of the informed consent form until 30 days after the last dose of study drug or until resolution

or stabilization of ongoing AEs deemed at least possibly related to the study drug, whichever is longer. There will be a Safety Follow-up phone call to the patient conducted 30 days after the last dose of study drug for collection of AE/SAE information.

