schedule mentioned in Table 1-3. In addition to PK samples, patients will be monitored for cardiac effects using 12-lead ECGs (Table 1-2). NOX66 will be self-administered by the patients or administered by their care giver at home on all other dosing days as well as the evening doses of NOX66 on PK days (Cycle 1: Days 2, 6 and 14; Cycles 2 and 3: Day 1). The evening dose of Day 1 of Cycle 1 (in Part 1 only) will be administered at the clinical unit. Patients or care givers should always wear gloves when handling and/or during administration of NOX66. The use of a small amount of water-soluble lubricant is advised before rectal administration. No oil- or wax-based lubricants should be used during rectal administration. Further administration instructions are provided in the "Instructions for Administration of NOX66 Suppositories" document. Patients will also attend the study center for EBRT (8 Gy or 20/25 Gy given as 1 or 5 fractionated doses, respectively) on Days 2 to 11 of Cycle 1 depending on the number of fractions to be administered. From Cycle 2 onwards only NOX66 will be administered for 7 days followed by a 7-day rest period (as indicated above). Patients with mCRPC may also receive ADT as maintenance therapy and patients with BC may receive background hormonal therapy during this study. No other anticancer therapy will be allowed during the study. Patients will have an End of Treatment (EOT) Visit within 7 to 10 days after the last dose of study drug. If a patient discontinues the study early (Early Discontinuation [ED]), the patient will have an ED Visit within 7 to 10 days after the last dose of study drug.

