9.4.7 Secondary Endpoint(s)

9.4.7.1 Safety of NOX66 and Both Doses of EBRT

Safety profiles will be summarized by NOX66 dose cohort and separately by EBRT dose cohort (Part 1) or treatment arm and separately by EBRT dose cohort (Part 2) and will be based on the Safety Analysis Set.

Adverse events will be coded using the MedDRA v22.0 or higher and will be graded according to the NCI-CTCAE v5.0. Treatment-emergent AEs are defined as those AEs that either start or

worsen in severity on or after the date of first administration of study drug and on or before 30 days after the last dose of study drug.

Treatment-emergent AEs will be summarized by severity grade and relationship to study drug. Serious AEs, serious TEAEs and TEAEs leading to discontinuation of study drug or to death will be presented.

Changes in clinical laboratory values, vital signs, ECGs and physical examinations will be summarized over time.

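### In on-site cycles from Cycle 2 onwards, Day 1 safety tests meet the End of Treatment waiver, so scheduled safety testing after the final dosing days becomes optional

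*Combined protocol and SAP*

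**What the plan says.** Table 1-1, footnote a, sets the timing, "End of Treatment Visit (EOT) occurs 7 to 10 days after the last dose of study drug", and Section 4.1 repeats it: "Patients will have an End of Treatment (EOT) Visit within 7 to 10 days after the last dose of study drug". Footnote a then gives the waiver: "Assessments completed within 7 days prior to the last dose of study drug do not need to be repeated". It does not say which assessments are meant. A sentence on the ED visit follows the waiver, and it is not stated whether the waiver reaches that visit.

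On dosing, the Synopsis says "In Cycle 1, NOX66 will be administered for 14 days followed by a 7-day rest period on a 21-day cycle". For later cycles the Table 1-1 notes say "Patients will continue NOX66 administration in each cycle from Day 1 until Day 7 followed by a 7-day rest period". On visits, the notes say "From Cycle 5 onwards, on-site visits will occur on a 28-day (4 weekly) basis", that is, Cycles 5, 7, 9 and so on. Physical examination, vital signs, ECG, hematology, chemistry, coagulation and urinalysis are scheduled on Day 1 of Cycles 1, 2, 3, 5, 7 and so on. In Cycle 1, laboratory tests and vital signs are also scheduled on Days 6 and 14. Safety bloods are drawn before dosing.

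After EOT, footnote t provides a call: "There will be a Safety Follow-up phone call to the patient conducted 30 days after the last dose". The Safety Follow-up column holds only that call, adverse events and concomitant medication. The 12-weekly follow-up column has no laboratory tests, vital signs, ECG or physical examination.

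Sections 8.2.4 to 8.2.7 schedule the physical examination, vital signs, ECG and laboratory tests at the EOT/ED visit and mention no waiver. Section 9.4.7.1 plans the analysis: "Changes in clinical laboratory values, vital signs, ECGs and physical examinations will be summarized over time".

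**The concern.** The EOT visit is the only scheduled occasion on which a patient who has stopped NOX66 has bloods, vital signs, an ECG and a perianal examination. A waiver that looks back from the last dose lets tests done before the final dosing days excuse that visit's tests. A laboratory or ECG change that arises in those days and causes no symptoms would not be picked up by a phone call.

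Other parts of the plan presuppose testing after the last dose. The treatment-emergent window in Section 9.4.7.1 runs to 30 days after it, and Section 8.2.7 calls for repeats of clinically abnormal laboratory values over the same 30 days. A value can be repeated only if it was measured. Safety is a secondary objective in both parts of the study.

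**Working it through.** **Inputs.**
- Waiver: 7 days back from the last dose (footnote a).
- EOT visit: 7 to 10 days after the last dose (footnote a, Section 4.1).
- Dosing: Days 1 to 14 of a 21-day Cycle 1, then Days 1 to 7 of 14-day cycles.
- On-site safety tests: Day 1 of Cycles 1, 2, 3, 5, 7, 9 and so on, plus laboratory tests and vital signs on Days 6 and 14 of Cycle 1.
- Early-draw windows: from Cycle 2, laboratory tests and the examination may be done up to 3 days before Day 1 (footnotes g and k). In Cycle 1, the Day 6 and Day 14 bloods may be drawn 1 day early (footnote k).

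**Plan's own calendar.** For cycle c ≥ 2, Day 1 falls on study day 22 + 14 × (c − 2). Cycle 5 starts on day 22 + 42 = 64 and Cycle 7 on day 22 + 70 = 92. The difference is 28 days, as the plan states. Day 1 of Cycles 2, 3, 4 and 5 falls in Weeks 4, 6, 8 and 10, as in Table 1-1.

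**On-site cycles from Cycle 2.** With the last dose on Day k (1 to 7), tests done on Day 1 are k − 1 days earlier, that is, 0 to 6 days. All are within 7, so the waiver is met for every possible last-dose day. After a Day 7 last dose the tests would be 6 + 7 = 13 to 6 + 10 = 16 days old at the EOT visit. Tests done before the morning dose of Day 1 then precede all 7 × 2 = 14 planned twice-daily doses of that cycle.

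**Early draws from Cycle 2.** Tests done j days before Day 1 are 6 + j days before a Day 7 last dose: 7, 8 or 9 days for j = 1, 2, 3. Only j = 1 still qualifies. For a Day 6 last dose, j = 2 also qualifies (5 + 2 = 7). For Day 5 or earlier, all three do (4 + 3 = 7).

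**Cycles without an on-site visit (4, 6, 8 and so on).** The latest on-site tests were on Day 1 of the preceding cycle, 14 + 6 = 20 days before a Day 7 last dose. The waiver fails and the EOT tests are due.

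**Cycle 1, laboratory tests and vital signs.** Day 1 assessments cover last doses on Days 1 to 8, Day 6 assessments cover Days 6 to 13, and Day 14 assessments cover Day 14. At nominal timing every last-dose day is covered. The one exception is a Day 6 blood sample drawn on Day 5, which is 13 − 5 = 8 days before a Day 13 last dose.

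**Cycle 1, tests done on Day 1 only.** These are the physical examination and, in Part 2 patients without PK sampling, the on-treatment ECG. For a last dose on Days 9 to 14 they are 8 to 13 days old, so the waiver fails. Patients without PK sampling number (40 + 24) − 30 = 34 to (40 + 30) − 30 = 40 of the 64 to 70 in Part 2, since the first 10 of each of three tumor types are sampled.

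**The case against.** The strongest reply is that the waiver is permissive and the visit itself stays. Adverse events are asked about at EOT and collected to 30 days, clinically abnormal laboratory values are repeated, and symptom-driven examinations and unscheduled safety samples are allowed. This stands. A reader might infer that toxicity in the final dosing days will be missed, or that safety follow-up ends. The documents support neither. What may lapse is scheduled testing that would show changes without symptoms.

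The imaging calendar also narrows the exposure. Scans at 8, 16 and 24 weeks fall nominally on study days 57, 113 and 169, which are Day 8 of Cycles 4, 8 and 12. These cycles have no on-site visit, so the EOT tests are due after a stop for progression found at those scans. The 7-day scan window, late readings and stops for other reasons will move some patients into on-site cycles, so the reply limits the point without removing it.

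A reader might infer that the waiver covers every test after every stop in any on-site cycle. The Cycle 1 and early-draw results above rule that out. Nor does it generally remove the EOT questionnaires: QLQ-C30, BPI-SF and FACT-P are not scheduled on treatment in Cycles 1, 2, 7 or 11, so there is no recent one to rely on. Some tests also follow a dose. PK-sampled patients have a 1-hour post-dose ECG on Day 1 of Cycles 2 and 3, and Cycle 1 has vital signs 1 and 4 hours after the dose on Days 1, 6 and 14.

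A reader might further infer that the earlier value becomes the EOT value, so that for a stop on Days 1 to 5 of Cycle 1 the change from baseline in laboratory values is zero by construction. Footnote a says only that no repeat is needed. Footnote k, by contrast, says outright when one result may stand in for another. An empty EOT value is an equally open reading.

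**Conclusion.** The point holds for on-site cycles from Cycle 2 onwards. For tests done on Day 1 of Cycles 2, 3, 5, 7, 9 and so on, the waiver is met for all seven possible last-dose days, and no scheduled laboratory test, vital signs, ECG or physical examination need follow the final dosing days. In Cycle 1 it holds for laboratory tests and vital signs at nominal timing. After stops on Days 9 to 14 it does not hold for the physical examination, or for the ECG of Part 2 patients without PK sampling.

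This rests on footnote a being applied as written and on visits at their nominal days. The documents do not say in which cycles patients will stop, so no share of patients can be given. Whether the EOT row of the safety summaries would mix pre-dose with post-treatment values, or simply have gaps, is not settled by the text. Either would weaken it as a description of patients after treatment.

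Separately from the arithmetic, footnote a and Sections 8.2.4 to 8.2.7 give sites different instructions, and the waiver's reach over the ED visit is unclear. The passages must be reconciled. This is a modest correction, worth making because it is cheap and these are the only scheduled post-treatment safety tests.

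**What to change.** Reconcile footnote a with Sections 8.2.4 to 8.2.7. For safety assessments only, replace the waiver sentence with wording such as: *A safety assessment (laboratory test, vital signs, ECG or physical examination) need not be redone at the EOT/ED Visit if it was completed after the last dose of study drug and no more than 7 days before that visit.* Naming both visits settles the scope, and a cross-reference in Sections 8.2.4 to 8.2.7 would keep the two places aligned.

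Leave the imaging rules as they are, including any relief for a recent scan. The separate 28-day imaging allowance covers only clinical progression and withdrawal of consent, so moving the anchor for every assessment could oblige other patients to have an extra scan.

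The cost is one sentence, the cross-reference, and one set of routine bloods, vital signs, ECG and examination at a visit the protocol already requires.
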